#### 5.3 REPORTING PROCEDURES

All adverse events should be reported. Depending on the nature of the event the reporting procedures below should be followed. Any questions concerning adverse event reporting should be directed to the Chief Investigator in the first instance.

### 5.3.1 Non serious AEs

All such events, whether expected or not, should be recorded.

### 5.3.2 Serious AEs

An SAE form should be completed and faxed to the Chief Investigator within 24 hours. However, hospitalisations for elective treatment of a pre-existing condition do not need reporting as SAEs.

All SAEs should be reported to the NRES Committee London - Hampstead where in the opinion of the Chief Investigator, the event was:

- 'related', ie resulted from the administration of any of the research procedures; and
- 'unexpected', ie an event that is not listed in the protocol as an expected occurrence

Reports of related and unexpected SAEs should be submitted within 15 days of the Chief Investigator becoming aware of the event, using the NRES SAE form for non-IMP studies. The Chief Investigator must also notify the Sponsor of all SAEs.

Local investigators should report any SAEs as required by their Local Research Ethics Committee, Sponsor and/or Research & Development Office.

## 6. ASSESSMENT AND FOLLOW-UP

### Screening

Following informed consent study participants will give a full medical history, and medication history and will undergo a physical examination and ECG. Fasting blood tests will be sent to assess HbA1c, plasma glucose, urea and electrolytes, serum C-peptide, thyroid function test, 9 am cortisol and coeliac screen (tissue transglutaminase antibody). Women of childbearing age will have a urine pregnancy test. A Gold Score questionnaire will be completed. If participants meet the inclusion criteria they will complete a structured participant interview and Quality of Life Questionnaires. A type 1 diabetes structured education refresher will be delivered according to the study curriculum and data from the preceding 4 weeks will be downloaded from the participants capillary blood glucose monitor using the Diasend software.

### Run-in

Participants will then commence a 2 week run-in phase using the Dexcom G4 sensor with a blinded receiver which stores glucose data but does not make it available to the participant. During the run-in phase participants will wear a Dexcom G4 continuous glucose sensor in the

anterior abdominal wall. The sensor detects glucose in the interstitial fluid and is calibrated to capillary blood glucose values taken a minimum of twice daily. Sensors last seven days and participants will be instructed on how to remove a sensor and implant a new one. This run-in will provide baseline data on glucose control including frequency and severity of hypoglycaemia and information on subject's compliance with frequency of CGM use.

### **Randomisation**

Participants will then receive standardised CGM education for the Dexcom and Abbott devices from study staff and will be randomised to Libre or the Dexcom G5 system with receiver. All education will be delivered by the research nurse from a predefined curriculum and will be supported by independent written materials. Both the Libre and G5 systems will be used non-adjunctively (without capillary blood glucose verification before making a treatment decision, in accordance with product licences) but participants will be instructed to test their capillary blood glucose if symptoms of hypo- or hyperglycaemia occur, in case of sensor failure or if the sensor glucose is out of the desired range. Participants will use the G5 sensor with the accompanying receiver and will change sensor every seven days (or sooner in the event of sensor failure). Real-time glucose data will be available to participants. Participants will use the Libre sensor with the accompanying receiver and will change the sensor after 14 days (or sooner in the event of sensor failure). Participants will be enabled to use the Libre monitor to assess glucose value and trend as often as they choose.

### **Follow-Up**

There will be a telephone visit 2 weeks after randomisation with a short, structured interview focusing on the function of the technology and any difficulties with use.

Participants will attend the clinical research facility 4 weeks after randomisation and data will be downloaded from their CGM device and self-monitoring using the Diasend software. At 8 and 16 weeks after randomisation participants will attend the clinical research facility and will have a blood test for HbA1c. They will additionally complete a Gold Score questionnaire, repeat the Quality of Life questionnaires, undergo a semi-structured interview conducted by the research team and data will be downloaded from their CGM device and capillary blood glucose monitor.

After 8 weeks all participants will be offered the opportunity to continue with the Dexcom G5 system for a further 8 week period. The G5 system in the follow-on may be used with the Dexcom receiver or Apple iOS smartphone application and will focus on usability, psychosocial outcomes and qualitative interviews. Participants will change the G5 sensor every seven days (or sooner in the event of sensor failure).

The participants will be provided with a contact number for technical support but insulin titration decisions will be made by the participant.

Quality of life, CGM-related treatment satisfaction and fear of hypoglycaemia data will be collected by mixed quantitative and qualitative methodologies. Validated (Problem Area in Diabetes (PAID), Glucose Monitoring System Satisfaction Survey (GMSS), Hypoglycaemia Fear Survey-II (FHS-II)) and non-validated questionnaires will be used and scripted interviews with participants will be undertaken by the research team to assess the impact of the technology on everyday living with type 1 diabetes. Gold questionnaire will be used to assess impact on hypoglycaemia awareness.

Low glucose alert settings will be standardised at 4.4 mmol/L (80mg/dL) for all participants at the start of the study and can be reduced to 4 mmol/L (70mg/dL) at week 2 depending during

the telephone visit depending on participant preference. High glucose alerts may be personalised.

The study will be completed at the end of the 8 week open label period.

## **7. STATISTICS AND DATA ANALYSIS**

With 40 participants, we can demonstrate as significant at 80% power a mean difference in time in hypoglycaemia between Libre and G5 of 0.45 standard deviations. Any smaller difference will be distinguished as signifying no significant difference between Libre and CGM. To allow for a 10-15% drop out, 45 participants will be recruited. Randomisation will be stratified by HbA1c quartiles (5-6%, 6.1-7.0%, 7.1-8.0% and 8.1-9%). Randomisation will be done using sealedenvelope.com.

Baseline data will be taken from the first 14 days of monitoring and outcomes will be calculated from the last 30 days in each treatment period.

Analysis will be by intention to treat. The primary outcome will be assessed by two-tailed unpaired t-test. For secondary outcomes parametric data will be compared between the two study arms by two-tailed unpaired t-test for continuous variables. Non-parametric data will be compared using a Kruskal Wallis test.

Data and all appropriate documentation will be stored for a minimum of 10 years after the completion of the study, including the follow-up period.

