## STUDY SUMMARY

**TITLE** Impact on Hypoglycaemia Awareness of Real Time CGM and Intermittent Continuous Glucose Data

**DESIGN** Randomised open-label parallel group study

**AIMS** This study aims to assess the impact of real-time continuous glucose monitoring and intermittently viewed continuous glucose data on frequency, duration and severity of hypoglycaemia in people with type 1 diabetes and impaired awareness of hypoglycaemia.

[figure not shown]
**OUTCOME MEASURES** The primary outcome is percentage of time spent in hypoglycaemia (<3.3mmol/L, 60mg/dL) measured by a continuous glucose sensor. Secondary outcomes include other measures of hypoglycaemia, overall glucose status and patient reported quality of life.

**POPULATION** Adults with type 1 diabetes and impaired hypoglycaemia awareness

**ELIGIBILITY** Participants identified in type 1 diabetes clinics and by recruitment from existing databases.

**DURATION** 18 weeks

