## 1.2 RATIONALE FOR CURRENT STUDY

This clinical study proposes to assess the impact of Libre on frequency, duration and severity of hypoglycaemia, compared with non-adjunctive use of the Dexcom G5 real-time CGM and will focus on people with impaired awareness of hypoglycaemia.

Hypothesis: Libre intermittent CGM has an equivalent impact on hypoglycaemia to real-time CGM.

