## 2. STUDY OBJECTIVES

**Primary outcome:** % time spent in hypoglycaemia (<3.3mmol/L, 60mg/dL)

**Secondary outcome:** % time spent in hypoglycaemia (<2.8mmol/L, 50mg/dL)  
% time spent in hypoglycaemia (<3.9mmol/L, 70mg/dL)  
% time in euglycaemia (3.9-7.8mmol/L, 70-140mg/dL)  
% time spent in target (3.9-10mmol/L, 70-180mg/dL)  
% time spent in hyperglycaemia (>10mmol/L, 180mg/dL)  
Number hypoglycaemic excursions  
Severe hypoglycaemia (requiring third party assistance to treat)  
MAD%  
Glucose variability  
HbA1c  
Sensor usage (compliance)  
Sensor life and % of sensor failure  
% of reported sensor readings compared to total possible readings  
Change in insulin dosage  
Diabetes treatment satisfaction  
CGM usability  
Diabetes quality of life  
Fear of hypoglycaemia  
Healthcare professional qualitative feedback

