## 3. STUDY DESIGN

Randomised parallel group trial over 18 weeks in 40 adult participants with type 1 diabetes and impaired hypoglycaemia awareness

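### The only stated hypothesis is equivalence, but the plan tests for no difference, sets no margin, and uses a 0.45 SD cut-off that is not the test's threshold

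*Combined protocol and SAP*

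**What the plan says.** - **Hypothesis (section 1.2).** "Libre intermittent CGM has an equivalent impact on hypoglycaemia to real-time CGM". No other hypothesis appears in the document. The aim in the Study Summary is neutral: "This study aims to assess the impact of real-time continuous glucose monitoring and intermittently viewed continuous glucose data".
- **Primary analysis (section 7).** "The primary outcome will be assessed by two-tailed unpaired t-test". Kruskal-Wallis is named for non-parametric data; it too is a test of no difference.
- **Sample size (section 7).** For a total sample of 40, the claim is: "we can demonstrate as significant at 80% power a mean difference in time in hypoglycaemia between Libre and G5 of 0.45 standard deviations".
- **Interpretation (section 7, next sentence).** "Any smaller difference will be distinguished as signifying no significant difference between Libre and CGM".

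The document contains no equivalence margin, in percentage of time or in SD units. It has no two one-sided tests, no confidence-interval rule, no alpha, no allocation ratio and no SD for the primary outcome.

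**The concern.** There are two linked faults.

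First, the analysis does not match the hypothesis. Equivalence is shown when a confidence interval for the difference lies wholly inside a margin fixed in advance. A t-test of no difference has no margin. If it is non-significant, the difference may be small or the trial may simply be imprecise.

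Second, the interpretive sentence takes the difference the trial is said to detect with 80% power and uses it as the line below which there is no significant difference. A detectable difference and a test's significance threshold are different quantities, so the sentence and the t-test can give different answers on the same data.

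The plan does not say that a null result will be called equivalence. But equivalence is the only hypothesis, so a null result is the one that would be read as supporting it. The outcome is time in hypoglycaemia, and participants are selected for impaired awareness or a recent severe event. A mistaken conclusion that the devices are interchangeable would therefore matter.

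**Working it through.** **Inputs.** From the document: 40 participants in two parallel arms (section 3); 0.45 SD, 80% power and a two-tailed unpaired t-test (section 7). Assumed because not stated: two-sided 5%, 20 per arm, equal SDs, normal data. Differences are in SD units because no SD is given.

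**1. The plan's own figure.** Noncentrality = 0.45 / √(2/20) = 0.45 / 0.316 = 1.42. Noncentral-t power on 38 df is 28% (normal approximation 30%), not 80%. With 20 per arm, 80% power needs 0.91 SD. A paired or one-sample calculation with n = 40 comes close to the stated figure (noncentrality 0.45 × √40 = 2.85; power 79% by t, 81% by normal approximation), but that is not the planned design.

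**2. Where the t-test becomes significant.** Critical observed difference = t(0.975, 38) × √(2/20) = 0.640 SD, which is also the half-width of the 95% CI.

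| Assumption | Critical difference (SD) |
|---|---|
| 20 per arm, two-sided 5% | 0.64 |
| 22 and 23 | 0.60 |
| 19 per arm | 0.66 |
| 27 and 13 | 0.68 |
| 20 per arm, two-sided 10% | 0.53 |

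All exceed 0.45 SD. Under the paired n = 40 calculation the threshold would be 0.32 SD, so 0.45 SD is not the cut-off there either.

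**3. An observed 0.45 SD.** t = 0.45 / 0.316 = 1.42, p = 0.163. The 95% CI is 0.45 ± 0.64, or -0.19 to 1.09 SD. An observed difference of zero has a 95% CI of ±0.64 SD, which does not exclude 0.45 SD.

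**4. How often each reading of the sentence gives no significant difference.** Column A is a non-significant t-test (noncentral t; 0.95 at zero by construction). Column B is an observed difference below 0.45 SD (400,000 simulations). The last column is the share of trials with an observed difference of 0.45 to 0.64 SD: non-significant by the test, but outside the sentence's rule.

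| True difference (SD) | A: non-significant | B: observed below 0.45 | Readings disagree |
|---|---|---|---|
| 0 | 0.95 | 0.838 | 0.112 |
| 0.45 | 0.716 | 0.493 | 0.223 |
| 0.64 | 0.495 | 0.273 | 0.222 |
| 0.91 | 0.199 | 0.075 | 0.124 |

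**5. Could 40 participants show equivalence?** The margins below are assumptions, since the plan has none. Equivalence is declared when the CI lies within ± the margin. The true difference is zero, with 20 per arm (2,000,000 simulations).

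| Assumed margin (SD) | Power, 90% CI | Power, 95% CI |
|---|---|---|
| 0.45 | 0.6% | 0.02% |
| 0.6 | 18% | 4% |
| 0.8 | 60% | 39% |
| 1.0 | 86% | 74% |

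For a 0.45 SD margin and 80% power with a 90% CI, n per arm = 2 × ((1.645 + 1.282) / 0.45)² ≈ 85, or 170 evaluable. With a 95% CI it is about 104 to 105 per arm.

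**The case against.** The strongest reply is that section 1.2 is one informal sentence. If equivalent impact is read as no difference, it is simply the null hypothesis of the t-test, and a significant result would count against it. The aim is neutral, section 7 never mentions equivalence, and the 0.45 SD sentence sits in the sample-size paragraph, where it may only describe loosely what the trial is not expected to detect. On that view the p-value decides, and the 0.45 to 0.64 SD gap never comes into play.

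Some of this stands. The sentence is ambiguous, which is why both readings are shown above, and the harm depends on how a null result would be interpreted. But reading the hypothesis as a null leaves it as something the trial can never support. Without a margin, a significant t-test does not refute equivalence either, because a statistically detectable difference can still be unimportant. Reading the sentence as a remark on detectability does not rescue it, because 0.45 SD is not the detectable difference for this design.

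A second reply is that the sponsor could keep the hypothesis and add a margin. That is legitimate in principle. At this sample size, however, reasonable power needs a margin of roughly 1 SD, and nothing in the document justifies one that wide.

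The power error is a separate defect. Correcting it alone would still leave no margin and no equivalence test.

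**Conclusion.** The concern holds and should be fixed before analysis. The hypothesis, the primary test and the interpretive sentence do not fit together, and nothing elsewhere in the document reconciles them. A non-significant result is likely even with a real difference: about 72% of the time at 0.45 SD and 49% at 0.64 SD. The 0.45 SD line conflicts with the t-test in 11% to 22% of trials over the true differences examined. The probabilities rest on 20 per arm, two-sided 5%, equal SDs and normal data. The mismatch between hypothesis and test rests on none of these, and the threshold stayed above 0.45 SD under every alternative allocation, sample size and alpha tried for the unpaired test.

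**What to change.** 1. Delete the section 7 sentence on smaller differences.
2. Reword the section 1.2 hypothesis to match the planned test: *The impact on percentage of time below 3.3 mmol/L differs between Libre and G5.*
3. Add to section 7: *The primary result will be reported as the Libre minus G5 difference in percentage of time below 3.3 mmol/L with its 95% CI. A non-significant result will be reported as inconclusive and not as equivalence.*
4. Restate the power for the unpaired design: *With 20 per arm and two-sided 5%, power is 80% for a difference of 0.91 SD (about 28% for 0.45 SD).*
5. Make no equivalence claim at this sample size. If the sponsor wants one, the plan needs a justified margin in percentage of time, a confidence-interval rule and a sample size derived from them.

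Items 1 to 4 change only the wording of sections 1.2 and 7 and need no new data or visits. The cost is that the trial gives up an equivalence conclusion and must own a less favourable detectable difference, which will invite the question of whether 40 participants are enough.

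### The recruitment target of 45 keeps 40 participants only up to about 11% drop-out, not across the stated 10-15% range (minor)

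*Combined protocol and SAP*

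**What the plan says.** Section 7 (Statistics and data analysis) ties power to a fixed number: "With 40 participants, we can demonstrate as significant at 80% power". Two sentences later it sets the recruitment target: "To allow for a 10-15% drop out, 45 participants will be recruited". It gives no inflation formula and does not say which point of the 10-15% range produced 45.

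Section 3 (Study design) describes the trial as being "in 40 adult participants" and does not say whether these are recruited participants or participants with outcome data.

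On the analysis, section 7 specifies intention to treat, takes outcomes from the last 30 days of each treatment period, and says: "The primary outcome will be assessed by two-tailed unpaired t-test". It gives no method for participants who have no outcome data.

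**The concern.** The plain reading of the recruitment sentence is that 45 recruits will leave the 40 participants needed for power if drop-out falls anywhere between 10% and 15%. Dividing 40 by the retained fraction shows that this is true only near the bottom of the range.

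What is at stake is the accuracy of a stated design allowance. An ethics committee, a site or a later reader would take it that a 15% loss had been provided for. If that loss occurred, the analysed number would fall below the one on which the plan's power statement rests, although the plan implies that it would not.

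**Working it through.** **Inputs**

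- Number on which power rests: 40 (section 7; the same number appears in section 3).
- Recruitment target: 45 (section 7).
- Drop-out range: 10% to 15% (section 7).
- Test: two-tailed unpaired t-test (section 7).
- Significance level: not stated; 5% assumed.
- Allocation ratio: not stated; 1:1 assumed.

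The two assumptions matter only for step 4.

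**Step 1. Reproduce the plan's 45.** With drop-out *d*, the number to recruit is 40/(1 − *d*), rounded up.

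- *d* = 10%: 40/0.90 = 44.4, so 45. This matches the plan.
- *d* = 12.5%: 40/0.875 = 45.7, so 46.
- *d* = 15%: 40/0.85 = 47.06, so 48. (With 47 recruits, 47 × 0.85 = 39.95, just under 40.)

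The shortcut 40 × (1 + *d*) gives 44 at 10%, 45 at 12.5% and 46 at 15%. So 45 can come from the correct formula at the lower end or from the shortcut at mid-range. Neither gives 45 at 15%.

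**Step 2. What 45 recruits leave.** Expected number remaining = 45 × (1 − *d*).

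| Drop-out | Remaining of 45 | At least 40? | Recruits needed for 40 |
|---|---|---|---|
| 10% | 40.5 | yes | 45 |
| 11.1% | 40.0 | yes (limit) | 45 |
| 12.5% | 39.4 | no | 46 |
| 15% | 38.25 | no | 48 |

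**Step 3. Break-even.** 1 − 40/45 = 5/45 = 11.1%. Five extra recruits are 12.5% of 40, but drop-out is lost from the 45 who are recruited, so 11.1% is the relevant fraction.

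**Step 4. Cost in power.** Suppose that the design had 80% power with 40 participants (20 per arm). For a two-sided 5% unpaired t-test, the noncentral t distribution puts the standardised difference with 80% power at 0.909. Holding that difference fixed and reducing the arms to 19 each (38 in total) gives power of 0.778. The loss is about 2 percentage points. The value 0.909 is used here only to measure that loss; it is not a figure from the plan.

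**The case against.** The strongest reply is that the sentence promises less than the plain reading takes from it. It does not say in terms that 40 are guaranteed at 15%, 45 is exactly right at 10%, and the shortcut gives 45 at the midpoint. This stands in part: 45 is not a failed calculation, and a reader who inferred that the target is wrong throughout would go further than the figures allow. But the sentence names the whole range, and neither formula makes 45 cover its upper end.

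A second reply is that drop-out is undefined and that intention to treat keeps people in. Section 8.2 (Consent) does keep participants who are switched to alternative treatment in follow-up and analysis, so stopping a device need not remove anyone. However, the primary outcome needs sensor data from the end of the treatment period, and the plan has no method for participants without such data. They add nothing to the t-test as written.

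A third reply is that the effect is too small to matter. It is small, and this point should carry no more weight than that. A reader might infer that the shortfall leaves the trial materially underpowered; about two participants and two points of power do not support that.

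A reader might also infer that sections 3 and 7 contradict each other on sample size. They need not: the 40 in section 3 agrees with the basis for power in section 7, and 45 is the recruitment figure. The label is missing, not the logic.

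Finally, the difference that the plan attaches to 40 participants ("between Libre and G5 of 0.45 standard deviations") raises a larger question. Under the same assumptions, power for 0.45 SD in an unpaired comparison is about 28% with 40 participants and 27% with 38. That is a separate issue. Settling it would not correct the drop-out sentence, and correcting the drop-out sentence would not settle it.

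**Conclusion.** The point holds as a minor error of statement. Forty-five recruits retain 40 participants up to 11.1% drop-out (5 of 45). At 15% about 38 remain, two short, and retaining 40 would take 48 recruits, three more than planned. These figures use only the plan's own numbers and treat drop-out as loss of outcome data.

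The power cost, from 80% to about 78%, is conditional. It supposes that the design has 80% power at 40, and it assumes a two-sided 5% level and 1:1 allocation, neither of which the plan fully states. It does not endorse 0.45 SD as the difference detectable with 40.

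**What to change.** Replace the recruitment sentence in section 7 with wording such as: *The recruitment target is 45, which allows for about 11% drop-out (5 of 45) while retaining 40 with outcome data; at 15% drop-out about 38 would remain.* In section 3, give the number as *40 with outcome data (45 recruited)*.

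Do not add a detectable difference for 38 participants on its own. Placed beside an unchanged 0.45 SD for 40, a figure from the unpaired t-test would make section 7 contradict itself. If the 0.45 SD statement is revised, give the figures for 40 and for 38 together, on the same stated significance level and allocation ratio.

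The cost is two wording changes and a slightly less favourable stated allowance. No extra participants are needed and trial conduct does not change. If the sponsor prefers to keep the full 10-15% range, the alternative is a target of 48, at the cost of three more recruits.

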### **8.2 CONSENT**

Consent to enter the study must be sought from each participant only after a full explanation has been given, an information leaflet offered and time allowed for consideration. Signed participant consent should be obtained. The right of the participant to refuse to participate without giving reasons must be respected. After the participant has entered the study the clinician remains free to give alternative treatment to that specified in the protocol at any stage if he/she feels it is in the participant's best interest, but the reasons for doing so should be recorded. In these cases the participants remain within the study for the purposes of follow-up and data analysis. All participants are free to withdraw at any time from the protocol treatment without giving reasons and without prejudicing further treatment.

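### Section 7's last-30-days window exempts no outcome, so as written it drops 26 of 56 randomised days (46%) for severe hypoglycaemia and for sensor usage, life and failure

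*Combined protocol and SAP*

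**What the plan says.** Section 7 (Statistics and Data Analysis) takes baseline data from the first 14 days of monitoring and then gives one rule for results: "outcomes will be calculated from the last 30 days in each treatment period". It names no outcome and makes no exception.

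Section 2 (Study Objectives) lists the secondary outcomes. Among them are severe hypoglycaemia needing third-party help, sensor usage, and "Sensor life and % of sensor failure". Neither Section 2 nor any other section gives these a window of their own.

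The randomised comparison lasts 8 weeks. Section 6 (Follow-Up) states: "After 8 weeks all participants will be offered the opportunity to continue with the Dexcom G5 system for a further 8 week period".

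Three other provisions bear on the point:
- Section 7: "Analysis will be by intention to treat".
- Section 8.2, on participants given alternative treatment: "In these cases the participants remain within the study for the purposes of follow-up and data analysis".
- Section 5.3: "All adverse events should be reported", with no 30-day limit.

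Section 6 and Appendix 1 schedule CGM downloads at weeks 4 and 8, so sensor data from the first month are collected.

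**The concern.** A late window suits glucose percentages, where the aim is to describe a settled state after participants have learned the device. It does not suit a count of rare events, where information grows with time at risk. Nor does it suit device outcomes, where early failures and early stopping are part of what is being measured.

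Severe hypoglycaemia matters in this trial: the stated aim includes the severity of hypoglycaemia, and a severe event in the past year is one of the two routes to entry. An analyst who follows Section 7 literally gives up nearly half the randomised exposure for this outcome. One who does not must choose another window without guidance, possibly after seeing the data.

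Section 7 also gives no rule for a participant with no data, or only some, in the window. Section 4.4 allows withdrawal when glucose control worsens, so such gaps could be related to outcome.

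**Working it through.** The plan gives no figure for the exposure that the window keeps or loses, so there is none to reproduce on that point.

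**Inputs from the documents.** Window 30 days (Section 7). Randomised period 8 weeks = 56 days (Section 6, Follow-Up). Planned number 40, recruited 45, dropout 10-15% (Section 7). Scheduled wear 7 days for G5 and 14 days for Libre (Section 6, Randomisation).

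**Assumptions.** Constant event rate. Window fixed at days 27-56. Dropout spread evenly over the 56 days. Severe-event rates of 0.5, 1 and 3 per person-year, because the documents give none.

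1. *Exposure lost per completer.* 56 - 30 = 26 days; 26/56 = 46.4%.

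2. *Person-years for 40 completers.* Full period: 40 x 56/365.25 = 6.13. Window: 40 x 30/365.25 = 3.29.

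3. *Precision.* At a constant rate, the standard error of a log event rate is proportional to 1/sqrt(exposure). The ratio is sqrt(56/30) = 1.37, about 37% larger.

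4. *Expected severe events, both arms together* (rate x person-years):

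| Assumed rate per person-year | 56 days | 30 days |
|---|---|---|
| 0.5 | 3.1 | 1.6 |
| 1 | 6.1 | 3.3 |
| 3 | 18.4 | 9.9 |

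5. *Scheduled sensor wears.* G5 has 56/7 = 8 wears: three end before day 27, one (days 22-28) straddles the start of the window, and four lie wholly inside. Libre has 56/14 = 4 wears: one ends before day 27, one (days 15-28) straddles, and two lie wholly inside. The plan does not say how a straddling sensor counts towards life or failure.

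6. *Early stoppers with no window data.* Dropout of 10-15% of 45 is 4.5 to 6.75 people. With even timing, those stopping by day 26 number 4.5 x 26/56 = 2.1 to 6.75 x 26/56 = 3.1. A constant dropout hazard gives 2.1 to 3.3. The remainder, roughly 2.4 to 3.6 people, contribute part of a window.

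7. *Direction of any effect on usage.* Take a participant with perfect use who stops at day 21. If days after stopping count as non-use, usage is 0/30 = 0% in the window and 21/56 = 37.5% over the full period, so the window penalises early loss. If the participant is instead left out as missing, the window hides early loss. The sign depends on a missing-data rule that the plan does not give.

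**The case against.** The strongest reply is that the rule was never meant for these outcomes. The sentence pairs the 30-day window with a baseline taken from 14 days of monitoring, which reads naturally as a rule for sensor readings. It cannot be literal for everything, since HbA1c, the Gold score and the questionnaires are taken at visits. This stands in part: the reach of the rule is inferred from a generic word, and less securely for severe hypoglycaemia than for sensor usage. But no section supplies the alternative window that the reply needs.

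A second reply is that nothing is lost for safety, because adverse events are reported throughout. That is correct as far as it goes: a severe event in week 2 is still on record. Adverse event reporting is not the between-arm analysis of the secondary outcome, however, and it does not set the period for that analysis.

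A third reply is that at 0.5 to 1 event per person-year even the full period yields only about 3 to 6 events, too few for a useful comparison. This also stands, and it limits the practical gain for severe hypoglycaemia. It is no reason to discard nearly half of what little information there is.

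A reader might infer that the window excludes everyone who stopped early. The documents do not support that. Analysis is by intention to treat, and Section 8.2 keeps participants given alternative treatment in follow-up and analysis. Under a window fixed at days 27-56, only those stopping by day 26 have no window data. If the window means the last 30 days of available data, early stoppers still contribute; the plan does not say which is meant.

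**Conclusion.** The point holds as one about secondary outcomes. As written, Section 7 applies a steady-state window to event and device outcomes and so leaves out 46% of each completer's randomised time. The cost is a standard error about 37% larger for a log event rate (constant rate assumed), half the scheduled sensor wears not wholly inside the window in each arm, and about 2 to 3 of 45 participants with no window data (even dropout timing and a fixed window assumed).

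A reader might go further and conclude that the rule flatters both devices, or favours the one that loses more people early. The documents do not support this. The effect on usage can run either way, and the scheduled wears split in the same proportions in both arms, so no difference between devices is shown. The primary outcome is a sensor glucose percentage, for which a late window is reasonable.

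**What to change.** Amend the sentence in Section 7 so that the last-30-days window applies only to sensor glucose outcomes: percentage of time in each range, excursions and variability. Add that severe hypoglycaemia, sensor usage, sensor life and sensor failure are analysed from randomisation to week 8 in all randomised participants, with days after stopping the device counted as non-use and the sensor in place at stopping included. Starting at randomisation also removes the straddling sensor at the opening of the window.

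The cost is a sentence or two. The data come from adverse event reporting and the week 4 and week 8 downloads already planned. The primary analysis and the sample size are unchanged.
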